### 7.2 Handling of Dropouts or Missing Data

Missing data will not be imputed.

#### 7.2.1 Handling of incomplete dates for AE

Imputation rules for missing or partial AE start date are defined below:

### **If only Day of AE start date is missing:**

If the start date has month and year but day is missing, the first day of the month will be imputed

- If this date is earlier than the first dose date, then the first dose date will be used instead.
- If this date is later than the stop date (possibly imputed), then the stop date will be used instead.

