6.1.5 Adverse Events

6.1.5.1 Definitions of Adverse Events

The investigator is responsible for reporting all TEAEs that are observed or reported during the study, regardless of their relationship to the investigational product or their clinical significance.

An AE is defined as any untoward medical occurrence in a patient enrolled into this study regardless of its causal relationship to the investigational product. The patient's legal representative (parent[s]/caregiver[s]) will be instructed to contact the investigator at any time if any symptoms develop.

A TEAE is defined as any event not present before exposure to the investigational product or any event already present that worsens in either intensity or frequency after exposure to the investigational product.

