6.1.5.3 Eliciting and Documenting Adverse Events

Adverse events will be assessed from the time the patient's legal representative (parent[s]/caregiver[s]) signs the ICF until and including the Follow-Up visit, 14 days after the last dose of the investigational product.

Serious AEs that occur more than 14 days after the last dose of the investigational product need not be reported unless the investigator considers them related to the investigational product.

At every study visit, the patient's legal representative (parent[s]/caregiver[s]) will be asked a standard nonleading question to elicit any medically-related changes in the patient's well-being. They will also be asked if the patient has been hospitalized, had any accidents, taken any new medications, or changed concomitant medication regimens (both prescription and OTC medications).

In addition to patient observations, AEs identified from any study data (e.g., laboratory values, physical examination findings, and ECG changes) or identified from review of other documents (e.g., seizure diaries) that are relevant to patient safety will be documented on the AE page in the eCRF.

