6.1.5.4 Reporting Adverse Events

All AEs reported or observed during the study will be recorded on the AE page in the eCRF. Information to be collected includes drug treatment, dose, event term, time of onset, investigator-specified assessment of severity and relationship to the investigational product, time of resolution of the event, seriousness, any required treatment or evaluations, and outcome. Adverse events resulting from concurrent illnesses, reactions to concurrent illnesses, reactions to concurrent medications, or progression of disease states must also be reported. All AEs will be followed to adequate resolution. The Medical Dictionary for Regulatory Activities (MedDRA) will be used to code all AEs.

Any medical condition that is present at the time that the patient is screened but does not deteriorate should not be reported as an AE. However, if it deteriorates at any time during the study, it should be recorded as an AE.

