13.1 Appendix: Schedule of Events

Table 13-1 Schedule of Events

Procedure	Screening Period	Treatment Period 1						Treatment Period 2: Dose Tapering Period	Follow-Up
		Visit 1	Visit 2	Telephone Contact	Visit 3	Telephone Contact	Visit 4		
Visit	Visit 1	Visit 2	Telephone Contact	Visit 3	Telephone Contact	Visit 4	Visit 5	Visit 6 / Early Termination Visit	Visit 7
Study Days	-28 to -6	1	2 to 6 ^a	7	12 or 13 or 14 ^a	21	28	42	56
Visit Window				± 2 days		± 2 days	± 2 days	± 5 days	± 5 days
Informed consent	X								
Medical history	X								
Inclusion/exclusion criteria	X								
Video EEG ^b	X						X		
BASED Score	X						X		
Demographics	X								
12-lead electrocardiogram	X			X			X	X	
Urine drug screen ^c	X								
Physical and neurological examination ^d	X	X	X ^e	X		X	X	X	X
Vital sign measurements ^f	X	X		X		X	X	X	X
Clinical laboratory tests ^g	X			X			X	X	
Investigational product administration ^h		X	X	X	X	X	X		

Procedure	Screening Period	Treatment Period 1						Treatment Period 2: Dose Tapering Period	Follow-Up
		Visit 1	Visit 2	Telephone Contact	Visit 3	Telephone Contact	Visit 4		
Visit	Visit 1	Visit 2	Telephone Contact	Visit 3	Telephone Contact	Visit 4	Visit 5	Visit 6 / Early Termination Visit	Visit 7
Study Days	-28 to -6	1	2 to 6 ^a	7	12 or 13 or 14 ^a	21	28	42	56
Visit Window				± 2 days		± 2 days	± 2 days	± 5 days	± 5 days
Dispensing of investigational product		X		X		X	X		
Investigational product accountability assessment				X		X	X	X	X
Adverse event monitoring		X	X	X	X	X	X	X	X
Review of prior and concomitant medications ^j	X	X	X	X		X	X	X	X
Clinical Global Impression of Change ^m		X		X		X	X	X	
Seizure diary ^j	X	X	X	X	X	X	X	X	
Pharmacokinetic blood sampling ^k		X				X			
Pharmacokinetic urine sampling ^l		X				X			

Abbreviations: EEG, electroencephalogram

- The investigator or his/her delegate will follow-up by telephone or email on Day 2 to Day 6 to ensure that the seizure diary is being completed, to review seizure counts, and to conduct daily assessments. The investigator will also contact the parent/caregiver by telephone on Day 12, or Day 13 or Day 14 to review seizure counts and to assess the patient's status.
- An overnight video-EEG will be completed within the Screening Period (Days -28 to -6), and repeated at Day 28 (Visit 5 [± 2 days]), [REDACTED]
[REDACTED]
- Urine drug screen assessment to test for the presence of cannabinoids will be performed locally.

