### **3.8 Evaluation of Treatment Safety**

#### **3.8.1 Adverse Events**

An AE is defined as any untoward medical occurrence in a patient enrolled into this study regardless of its causal relationship to the investigational product. The patient's legal representative (parent[s]/caregiver[s]) will be instructed to contact the investigator at any time if any symptoms develop.

A TEAE is defined as any event not present before exposure to the investigational product or any event already present that worsens in either intensity or frequency after exposure to the investigational product.

All AEs will be reported or observed during the study will be recorded on the AE form in the eCRF. The AE and SAE reporting period begins after administration of study drug through the follow up visit. The Investigator will follow-up on all AEs observed or reported by the subject up to the end of the reporting period unless the event stabilizes and follow-up is no longer necessary. The Investigator will follow-up on SAEs until they are considered resolved or the outcome is known.

The following details will be collected for AEs: description of the AE, onset date/time, action taken with study drug (dose not changed, drug interrupted, drug withdrawn, dose increased, not applicable, or unknown), date/time of resolution, any additional treatment given, outcome

(recovered/resolved, not recovered/not resolved, recovered/resolved with sequelae, recovering/resolving, fatal or unknown), severity (mild, moderate, severe), seriousness (yes, no), relationship to study drug (unrelated, possibly, probably, definitely related or unknown), and whether the AE causes early termination of the subject.

The severity of AEs will be categorized as follows:

- Mild: These events require minimal or no treatment and do not interfere with the patient's daily activities.
- Moderate: An AE that is sufficiently discomforting to interfere with normal activities.
- Severe: These events interrupt a patient's usual daily activity and may require systemic drug therapy or other treatment. Severe events are usually incapacitating.

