### **If Year of AE start date is missing:**

If the year of AE start is missing or AE start date is completely missing then query site with no imputation. Also compare the full (or partial) AE end date to the first dose date. If the AE end date is before the first dose date then the AE should be considered as a pre-treatment AE. Otherwise, the AE will be considered as TEAE.

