## 7.12 Analysis of Safety Data

### 7.12.1 Adverse Events

All AEs will be coded to SOC and PT using Medical Dictionary for Regulatory Activities (Version 22.0 or later) and presented by subject in data listings.

A treatment-emergent adverse event (TEAE) is defined as any AE that began or worsened following the start of dosing of Treatment Period 1, Day 1 to Follow-Up.

A treatment-related AE is defined as any TEAE that is assessed by the Investigator as possibly, probably or definitely related to study drug.

Adverse event analyses will be conducted using the Safety Population.

The overall incidence of TEAEs (number and percentage of subjects) as well as the number of events will be summarized for mild TEAEs, moderate TEAEs, severe TEAEs, TEAEs assessed as at least possibly related, SAEs, TEAEs leading to study or drug discontinuation, SAEs related to study drug, life-threatening SAEs and SAEs resulting in death. All AE reports will also include the action taken as a result of the AE such as dose not changed, drug interrupted, drug withdrawn, dose increased, not applicable, or unknown.

The following TEAEs summaries will be presented (where applicable the number of patients (%)) and number of events will be summarized) by SOC and PT for overall treatment group:

- TEAEs
- Treatment-related TEAEs
- TEAEs leading to investigational product discontinuation
- Treatment-related TEAEs leading to investigational product discontinuation
- Serious TEAEs
- Treatment-related serious TEAEs
- TEAEs leading to death
- Treatment-related TEAEs leading to death.

All TEAEs will be summarized by SOC and PT using frequency counts and percentages (i.e., number and percentage of patients with an event); also the number of events will be presented

Tabulations will include an overall incidence of subjects reporting at least one AE, an overall incidence of TEAEs, and incidence within SOC and PT. Each patient may only contribute once (i.e., most severe occurrence) to each of the incidence rates, regardless of the number of occurrences.

For the incidence at the subject level by SOC, PT and relationship to study drug; if a subject experiences more than 1 event within the same SOC and PT, only the most related occurrence (in

descending order of definitely related, probably related, and possibly related) will be included in the incidence.

Listings of AEs, TEAEs, SAEs, TEAEs leading to death and TEAEs leading to study drug discontinuation will also be presented.

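### Minor: SAP 7.2.1 can turn an adverse event known to have begun before dosing into a Day 1 TEAE

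*SAP*

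**What the plan says.** SAP 7.2.1 has three branches for incomplete AE start dates.

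- **Day missing:** impute the first of the month, then "If this date is earlier than the first dose date, then the first dose date will be used instead". A second bullet caps the result at the stop date.
- **Day and month missing:** impute 1 January, then apply the same two bullets.
- **Year missing:** no imputation. The end date is compared with first dose: "If the AE end date is before the first dose date then the AE should be considered as a pre-treatment AE". Otherwise the AE is a TEAE.

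The Protocol (6.1.5.1) counts a pre-existing event as a TEAE only if it is "any event already present that worsens in either intensity or frequency after exposure to the investigational product". In SAP 7.12.1 a TEAE "is defined as any AE that began or worsened following the start of dosing of Treatment Period 1, Day 1 to Follow-Up".

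The documents disagree on when AE collection starts. Protocol 6.1.5.3 has: "Adverse events will be assessed from the time the patient's legal representative" gives consent. SAP 3.8.1 has: "The AE and SAE reporting period begins after administration of study drug through the follow up visit". In the schedules of both documents (Protocol Table 13-1, SAP Table 3-1) the row "Adverse event monitoring" has no entry at Visit 1 and begins at Visit 2.

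**The concern.** Moving a partial date to first dose is a sensible cautious default when the onset could lie on either side of dosing. The rule as written goes further. It also moves dates whose recorded month, or recorded year, ended before dosing, where the record already settles that onset was pre-dose. An AE that began before dosing, did not worsen, and is ongoing, has no stop date, or stopped on or after first dose then becomes a Day 1 TEAE.

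Equivalent records are also treated differently. With first dose on 10 June, a complete onset date of 31 May is pre-treatment, while May with no day is treatment-emergent.

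TEAE incidence is the primary endpoint in the Protocol synopsis, and this error can only raise it.

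**Working it through.** **1. The rule on test dates.** First dose 10 June 2021 (chosen for illustration), no worsening, bullets applied in the order written. The corrected rule moves the date to first dose only if the recorded month and year are those of first dose.

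| Recorded onset | Stop | SAP 7.2.1 | Corrected rule |
|---|---|---|---|
| May 2021 | ongoing | 10 Jun, TEAE | 1 May, pre-treatment |
| May 2021 | 25 Jun | 10 Jun, TEAE | 1 May, pre-treatment |
| May 2021 | 10 Jun | 10 Jun, TEAE | 1 May, pre-treatment |
| May 2021 | 20 May | 20 May, pre-treatment | 1 May, pre-treatment |
| June 2021 | ongoing | 10 Jun, TEAE | 10 Jun, TEAE |
| June 2021 | 5 Jun | 5 Jun, pre-treatment | 5 Jun, pre-treatment |
| July 2021 | ongoing | 1 Jul, TEAE | 1 Jul, TEAE |

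Year only, first dose 12 January 2021, AE ongoing: an onset recorded as 2020 becomes 12 January 2021 (TEAE) under the SAP and 1 January 2020 (pre-treatment) under the corrected rule. An onset recorded as 2021 becomes 12 January 2021 under both.

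The fourth row depends on the order of the bullets. If the stop-date bullet is read as testing the date first imputed (1 May, which is not later than 20 May), the cap does not act. The AE then starts on 10 June, after its own stop date, and is a TEAE.

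**2. How often the recorded month is an earlier one.** Assume onset is uniform over the W days before first dose and first dose is uniform over 365 calendar days. An onset k days before dosing (k up to 28) falls in an earlier month when first dose is on day k of the month or sooner, which is 12k of the 365 dates. Averaging over k = 1 to W gives 6(W+1)/365. For an earlier year the share is (W+1)/730. Screening runs from Day -28 to Day -6, so W is taken from 6 to 28.

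| W (days) | Earlier month | Earlier year |
|---|---|---|
| 6 | 42/365 = 11.5% | 7/730 = 1.0% |
| 14 | 90/365 = 24.7% | 15/730 = 2.1% |
| 28 | 174/365 = 47.7% | 29/730 = 4.0% |

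**3. Expected misclassified events in the trial.** If AEs are collected only after dosing, the answer is 0. If they are collected from consent, the exposed pool is new onsets between consent and first dose, because under Protocol 6.1.5.4 a condition "present at the time that the patient is screened but does not deteriorate should not be reported as an AE". The documents give none of the rates, so all are assumptions: 5 to 20 such AEs, day missing in 2–10%, persisting to dosing in 30–70%, not worsened in 50–100%.

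Expected events x = AEs × earlier-month share × day missing × persisting × not worsened:

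- Low: 5 × 0.115 × 0.02 × 0.3 × 0.5 = 0.0017
- Mid: 10 × 0.247 × 0.05 × 0.5 × 0.75 = 0.046
- High: 20 × 0.477 × 0.10 × 0.7 × 1.0 = 0.668

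The chance of at least one, 1 − exp(−x), is 0.2%, 4.5% and 48.7%.

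Year-only branch, with day and month both missing in 0.5–2% (assumed): low 5 × 0.010 × 0.005 × 0.3 × 0.5 = 0.00004; high 20 × 0.040 × 0.02 × 0.7 × 1.0 = 0.011.

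**4. Effect on incidence.** With 35 patients, and 80% having some other TEAE anyway (assumed), the expected change in overall TEAE incidence is x × 0.2/35: 0.001, 0.026 and 0.38 percentage points. In a 6–12 month subgroup of 7 (the planned minimum), with events spread evenly, x × 7/35 gives 0.0003, 0.009 and 0.13 events. If one patient is affected, the shift on that preferred term is 1/35 = 2.9 points overall, or 1/7 = 14.3 points in that subgroup.

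**The case against.** **No such AEs may be recorded.** SAP 3.8.1 and both schedules start collection after dosing or at Visit 2. Protocol 3.1 likewise describes TEAEs and SAEs being recorded from Visit 2. On that reading 7.2.1 never meets a new pre-dose AE. This stands as a condition but does not remove the point. Protocol 6.1.5.3 collects from consent, Protocol 7.7.1 lists non-treatment-emergent AEs, and the year-missing branch of 7.2.1 itself has a pre-treatment category.

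**The size is assumed and tiny.** This stands. Onset date is a required field and the data are queried, so missing days should be rare. The high case sets all five inputs to their extremes together, including a 28-day window for everyone, although the Protocol expects screening to be appreciably shorter.

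**Over-counting is the safer error, and the fix could cause under-counting.** A pre-dose AE would count only if its worsening is captured. Protocol 6.1.5.6 does not require each episode of an intermittent AE to be documented, and the listed AE fields have no item for worsening in frequency. In a seizure population that matters, so the fix must address it. But an AE with a complete pre-dose start date already carries the same dependence, and caution does not justify counting an AE known not to have worsened.

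**7.2.1 imputes dates and does not expressly assign TEAE status in these two branches.** This is true. That the imputed date sets the flag is an inference, though hard to avoid when SAP 7.12.1 defines a TEAE by when it began.

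**Conclusion.** The concern holds and is minor. As written, both partial-date branches can classify an unworsened AE as treatment-emergent when the record already shows pre-dose onset, contrary to Protocol 6.1.5.1 and SAP 7.12.1. The effect is none under post-dose collection. Under collection from consent it is about 0.05 events in the trial (0.002 to 0.67), on rates that are all assumed. The bias is upward only, all AEs are listed, and the Protocol plans no formal testing, so no conclusion of the trial is likely to change. It deserves correction because the rule gives a wrong classification on the primary endpoint and is easily put right.

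Two related gaps surfaced. The start of AE collection is contradictory and decides whether the error can occur at all. The stop-date bullet also allows for an imputed AE stop date although 7.2.1 gives no rule for one; the SAP's only stop-date convention is for medications (7.2.2).

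**What to change.** In SAP 7.2.1, before database lock:

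- Substitute the first-dose date only when the recorded month and year (or the year, if the month is missing) equal those of first dose. Otherwise keep the first of the month or 1 January, so that an earlier month or year makes the AE pre-treatment.
- State that the stop-date cap acts on the date after any move to first dose.
- State that a pre-dose AE recorded as worsening in intensity or frequency after dosing remains a TEAE, whether or not a severity change was recorded.
- Give an AE stop-date imputation rule, or compare a partial stop date with first dose as the year-missing branch does.

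Separately, reconcile Protocol 6.1.5.3 with SAP 3.8.1 and the two schedules on when AE collection starts.

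The cost is one condition in each of two branches and a few sentences in the SAP. Partial dates that are truly ambiguous still default to TEAE. A few fewer AEs may count as TEAEs, and worsening in frequency may need a site query in the few affected cases. Reconciling the collection start takes a sentence and perhaps one schedule entry, which may touch the Protocol.

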### **If Day and Month of AE start date are missing:**

If the start date has year, but day and month are missing, the 1st of January will be imputed

- If this date is earlier than the first dose date, then the first dose date will be used instead.
- If this date is later than the stop date (possibly imputed), then the stop date will be used instead.

### **If Year of AE start date is missing:**

If the year of AE start is missing or AE start date is completely missing then query site with no imputation. Also compare the full (or partial) AE end date to the first dose date. If the AE end date is before the first dose date then the AE should be considered as a pre-treatment AE. Otherwise, the AE will be considered as TEAE.

#### **7.2.2 Handling missing or partial Prior/Concomitant Medication Dates**

Missing or partial medication start date:

- a. If only DAY is missing, the first day of the month will be assumed.
- b. If DAY and Month are both missing, the first day of the year will be assumed.
- c. If DAY, Month and Year are all missing, the day before the first dose date will be assumed.

Missing or partial medication stop date:

- a. If only DAY is missing, the last day of the month will be assumed.
- b. If DAY and Month are both missing, the last day of the year will be assumed.
- c. If DAY, Month and year are all missing, ‘continuing’ status to stop date will be assigned.

### **7.3 Examination of Subgroups**

Additional subgroup summaries will be performed to determine whether differences exist in primary safety and efficacy endpoint results between subgroups.

The list of potential subgroups (with applicable definitions in parentheses) includes, but is not necessarily limited to, the following:

- Sex (Female vs. Male)
- Age (6-12 months; >12-24 months; >24-36 months)
- Concomitant anti-epileptic drugs (AEDs) (Specific categories to be finalized prior to database lock. The categories will be determined based upon which AEDs or combinations of AEDs the subjects take during the course of the study)

For each subgroup variable, the frequency and percentage will be displayed.

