3.1 Study Design

This is an open-label, multicenter study to evaluate the safety, tolerability, PK, and exploratory efficacy of the investigational product in children aged 6 months through 36 months with IS. Patients will receive the investigational product at a dose of 6 mg/kg orally BID; once in the morning and 12 hours following the morning dose during the first 7 days of Treatment Period 1. Starting from the PM dose on the day of Visit 3, the dose will be escalated and patients will receive the investigational product at a dose of 9 mg/kg orally twice daily. Starting on Day 15, the dose will be escalated again and patients will receive the investigational product at a dose of 15 mg/kg orally twice daily until the end of Treatment Period 1.

The overall study duration is expected to be up to 84 days (\pm 5 days). As illustrated in [Figure 3:1](#), the study is planned to include 4 periods: Screening Period (up to 28 days), Treatment Period 1 (28 days), Treatment Period 2 (Dose Tapering Period [14 days]), and a Follow-Up Period (14 days). There will be a total of 7 study visits and 6 telephone/email contacts. Overall, the study includes 3 overnight stays: one for screening procedures including video-electroencephalogram (EEG) recordings, one for Day 1 (Visit 2) PK sampling ([Section 6.2](#)) and AE monitoring, and one for Day 28 (Visit 5 [\pm 2 days]) video-electroencephalogram (EEG) recordings.

During the Screening Period, Treatment Period 1, and Treatment Period 2, no changes to dosages of any drugs used for treating epileptic seizures are permitted (except for rescue medications used for acute treatment of breakthrough seizures which are not known to be CYP3A4 substrates and whose PK has not been shown to be impacted in the presence of a CYP3A4 inhibitor [see [Appendix 13.3](#) for a non-exhaustive list of CYP3A4 substrates]). Changes of dosages of drugs used for treating epileptic seizures are permitted 2 or more days after the investigational product has been discontinued.

Screening Period (Days -28 to -6):

Eligible patients will complete all screening procedures and assessments within no more than 28 days before the start of Treatment Period 1. Refer to [Appendix 13.1](#) for the list of tests/procedures. The actual length of the Screening Period is expected to be appreciably

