5.7 Prior and Concomitant Medication

Use of all concomitant medications will be recorded in the patient's eCRF. This will include all prescription drugs, herbal products, vitamins, minerals and over-the-counter (OTC) medications. The minimum requirement is that the medication name and the dates of administration are to be recorded. Any changes in concomitant medications will also be recorded in the patient's eCRF. Use of drugs known to be CYP3A4 substrates and whose PK has been shown to be impacted in the presence of a CYP3A4 inhibitor (see [Appendix 13.3](#) for a non-exhaustive list of CYP3A4 substrates) will not be allowed during the Screening

Period, Treatment Period 1, and Treatment Period 2; use of drugs known to be CYP3A4 substrates and whose PK has been shown to be impacted in the presence of a CYP3A4 inhibitor will not be allowed until 2 or more days after the investigational product has been discontinued. Except for drugs known to be CYP3A4 substrates and whose PK has been shown to be impacted in the presence of a CYP3A4 inhibitor, concomitant medications for treating non-epileptic seizure disorders are acceptable but changes in dose(s) are discouraged. Concomitant drugs used for treating epileptic seizures will be allowed during the study (excluding felbamate, cannabinoids, and drugs used for treating epileptic seizures known to be CYP3A4 substrates and whose PK has been shown to be impacted in the presence of a CYP3A4 inhibitor) if the doses remain stable during the Screening Period, Treatment Period 1, and Treatment Period 2 (with the exception that rescue medications used for acute treatment of breakthrough seizures which are not known to be CYP3A4 substrates and whose PK has not been shown to be impacted in the presence of a CYP3A4 inhibitor may be administered at any time during the study). Changes of dosages of drugs used for treating epileptic seizures are permitted 2 or more days after the investigational product has been discontinued. Ketogenic diet and vagus nerve stimulation therapies will not be allowed during the Screening Period, Treatment Period 1, and Treatment Period 2; ketogenic diet and vagus nerve stimulation therapies will not be allowed until 2 or more days after the investigational product has been discontinued.

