### **3 STUDY DESIGN**

#### **3.1 General**

This is an open-label, multicenter study to evaluate the safety, tolerability, PK, and exploratory efficacy of the investigational product in children aged 6 months through 36 months with IS. Patients will receive the investigational product at a dose of 6 mg/kg orally twice daily (BID); once in the morning and 12 hours following the morning dose during the first 7 days of Treatment Period 1. Starting from the PM dose on the day of Visit 3, the dose will be escalated and patients will receive the investigational product at a dose of 9 mg/kg orally twice daily. Starting on Day 15, the dose will be escalated again and patients will receive the investigational product at a dose of 15 mg/kg orally twice daily until the end of Treatment Period 1. █

Table 3-1 Schedule of Event.

[figure not shown]
The overall study duration is expected to be up to 84 days ( $\pm$  5 days). As illustrated in [Figure 3-1](#), the study is planned to include 4 periods: Screening Period (up to 28 days), Treatment Period 1 (28 days), Treatment Period 2 (Dose Tapering Period [14 days]), and a Follow-Up Period (14 days). There will be a total of 7 study visits and 6 telephone/email contacts. Overall, the study includes 3 overnight stays: one for screening procedures, one for Day 1 (Visit 2) PK sampling and AE monitoring, and one for Day 28 (Visit 5 [ $\pm$  2 days]) video-EEG recordings.

During the Screening Period, Treatment Period 1, and Treatment Period 2, no changes to dosages of any drugs used for treating epileptic seizures are permitted (except for rescue medications used for acute treatment of breakthrough seizures which are not known to be CYP3A4 substrates and whose PK has not been shown to be impacted in the presence of a CYP3A4 inhibitor). Changes of dosages of drugs used for treating epileptic seizures are permitted 2 or more days after the investigational product has been discontinued.

The study design of the study is depicted in [Figure 3-1](#).

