## **7.7 Subject Demographics and Baseline Characteristics**

Subject demographic data and baseline characteristics will be summarized using descriptive statistics by overall treatment and will include the following parameters: sex, age, race, ethnicity, concomitant anti-epileptic drugs, height, weight, and body mass index (BMI). Demographic data and baseline characteristics will also be listed for safety population.

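### The concomitant-AED subgroups in SAP 7.3 rest on drugs taken during the study rather than at first dose, so membership can depend on outcome

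*SAP*

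**What the plan says.** SAP 7.3 plans subgroup summaries "to determine whether differences exist in primary safety and efficacy endpoint results between subgroups". Its three listed variables are sex, age and concomitant AEDs. Sex and age are fixed at entry. For AEDs the section says "Specific categories to be finalized prior to database lock" and then: "The categories will be determined based upon which AEDs or combinations of AEDs the subjects take during the course of the study". It gives no other rule for assigning a patient to an AED category.

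Several other sections bear on which drugs could count:

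- **Stability rule.** SAP 3.1 states that "no changes to dosages of any drugs used for treating epileptic seizures are permitted" during Screening and both treatment periods, with an exception for qualifying rescue medication. Protocol 4.1.2 (exclusion 14) also requires stable doses for at least 14 days before screening.
- **Rescue.** Under Protocol 5.7, rescue drugs for breakthrough seizures "may be administered at any time during the study", but only if they are not CYP3A4 substrates of the affected kind.
- **After study drug.** Protocol 3.1: "Changes of dosages of drugs used for treating epileptic seizures are permitted 2 or more days after the investigational product has been discontinued".
- **Recording.** SAP 7.12.6 counts a drug started on or after first dose as concomitant and sets no end date. The schedule of events in both documents records medications to the final Follow-Up visit.

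**The concern.** A subgroup variable should be settled before the outcome it is used to compare. Here an AED given because a patient had breakthrough seizures, responded poorly or had an adverse event could place that patient in a different category. The table would then show worse results in that category even if background AEDs made no difference.

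At stake is the reading of an exploratory table. In a small single-arm study, a difference by AED category may be carried into the design of later trials. One produced by the classification rule would mislead there. The rule is also loose enough that two programmers could produce different tables from the same data.

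**Working it through.** **1. Is there a baseline anchor elsewhere?** No. SAP 7.7 lists concomitant AEDs among the baseline characteristics but does not restrict them to drugs in use at first dose. SAP 7.12.6 includes later starts. Neither document defines AED for this purpose.

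**2. Where do the two definitions agree?** Stability is required from 14 days before screening to the end of Treatment Period 2. In a patient who follows the protocol, the non-rescue AEDs taken while on study drug are therefore the baseline AEDs. The definitions can differ only through rescue use, or after study drug stops.

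**3. The rescue route.** Protocol 5.7 bars affected CYP3A4 substrates, and Appendix 13.3 lists diazepam and midazolam among them, so the permitted set is narrower than all rescue drugs. What remains is given for breakthrough seizures. Protocol 6.1.5.2 names a doubling of seizure frequency over 7 days or longer as an example of a serious event. Rescue for such an event could let the adverse event itself alter the AED category.

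**4. The route after study drug.** The permission in Protocol 3.1 concerns dosages. A dose change does not alter which AEDs a patient takes; only a start or a stop does. New starts are nevertheless possible, because the bar on affected CYP3A4 substrates lifts at the same time (Protocol 5.7) and Appendix 13.3 includes an AED, carbamazepine.

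- Planned stop Day 42, plus 2 days = Day 44.
- To Follow-Up on Day 56: 56 − 44 + 1 = 13 days.
- To the end of the Visit 7 window, Day 56 + 5 = 61: 61 − 44 + 1 = 18 days.
- In early discontinuers the window opens 2 days after their own last dose.

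**5. Does this overlap the outcomes?** TEAEs are counted to Follow-Up (SAP 7.12.1). The Day 28 video-EEG is done before Day 44 in an open-label study. A drug added later cannot change that EEG, or the diary, which ends with study drug. It can still change the subgroup in which those results are compared.

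**6. Which summaries are exposed?** The efficacy analysis set (EAS) requires at least 26 days of treatment and a completed Day 28 EEG (SAP 7.4). Most early discontinuers fall outside it, so they mainly affect the safety subgroups. The efficacy subgroups are exposed through rescue use and through later additions in patients who reached Day 28.

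**7. Size.** The plan has no figure to reproduce and no rate of AED addition. The following only illustrates direction. Assume that AEDs truly have no effect on response, that the response rate is p, and that an AED is added with probability qN in non-responders and qR in responders.

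- Proportion with an AED added: a = p·qR + (1 − p)·qN
- Response if added: p·qR / a
- Response if not added: p·(1 − qR) / (1 − a)

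Example with p = 20%, qN = 40%, qR = 5%: a = 0.01 + 0.32 = 0.33. Response if added = 0.01/0.33 = 3.0%. Response if not added = 0.19/0.67 = 28.4%. The spurious difference is about 25 points.

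Difference in points (not added minus added), with qR = 5%:

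| p | qN = 20% | qN = 40% | qN = 60% |
|---|---|---|---|
| 9% | 8 | 12 | 18 |
| 20% | 17 | 25 | 35 |
| 30% | 24 | 35 | 47 |

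With qN = qR = 20% the difference is 0 at every p. Across the table, a runs from 0.155 to 0.550, so among 26 completers the added group would hold about 4 to 14 patients. The 9% is the response to nonstandard therapies cited in Protocol 1.2. All other rates are assumptions. SAP 7.3 does not define an added versus not-added split; that simplification is used here only to isolate the mechanism.

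**The case against.** The strongest reply is that SAP 7.3 describes how categories will be formed, not who belongs in each. It calls the subgroups potential, defers the specifics and does not mention rescue or post-treatment drugs. On that reading baseline therapy may be what is meant, and the stability rule makes the two definitions agree throughout dosing apart from rescue. The study is also descriptive: Protocol 7.7 rules out formal significance testing, SAP 7.3 promises only frequencies and percentages, and the SAP table list names no subgroup table.

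Much of this stands and limits the point. It does not remove it, because the sentence is the only rule offered and refers to the whole study.

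A second objection is that co-exposure arising during treatment matters for safety. That also stands. It argues for showing later AEDs separately, not for using them to define a subgroup.

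A reader might infer three stronger things that the documents do not support:

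- **That AEDs may change freely during the study.** They may not; see the stability rule and the limit on rescue drugs.
- **That patients who fail and stop early distort the efficacy subgroups.** Those treated for less than 26 days, or without the Day 28 EEG, are outside the EAS.
- **That the planning numbers measure reclassification.** The gap between about 35 enrolled and at least 26 completers is 9, and 9/35 = 25.7%. That is a planning allowance and says nothing about how many patients will have an AED added.

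**Conclusion.** The point holds in limited form. As written, SAP 7.3 lets AED subgroup membership depend on events after first dose, some of which may be responses to the outcomes being compared. The exposure is confined to qualifying rescue use and to AEDs started or stopped after study drug ends. Its size cannot be derived from the documents. It is zero if additions are unrelated to outcome, and the illustration shows only that it need not be small if they are related. No primary result or error rate is affected.

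This rests on reading the SAP 7.3 sentence as the membership rule, and on rescue and post-treatment drugs counting as AEDs because nothing excludes them. A baseline definition would not make subgroup differences into effects of background therapy, since baseline AEDs are not randomised.

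**What to change.** In SAP 7.3, define AED subgroup membership by the AEDs ongoing at first dose, excluding rescue medication and anything started after first dose. Base the groupings on those baseline data alone. Define AED, and use the same definition in SAP 7.7. Summarise rescue use and AEDs started after first dose separately, labelled as post-baseline information.

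The cost is a few lines of SAP text before database lock. SAP 3.8.6 already collects start and stop dates and indication, so both summaries can be derived. The text should say whether the imputation rules of SAP 7.2.2 apply, because a wholly missing start date is set to the day before first dose and would count as baseline. The small loss is that co-exposure arising during the study appears in the separate summary rather than in the subgroup tables. No treatment or concomitant-medication rule changes.
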